3.2.2 Length of Study

The length of the study for an individual patient will be:

- Screening period up to 4 weeks
- Treatment and observation period at least 24 weeks
- Safety follow-up visit 24 weeks after discontinuing emicizumab
- An extension phase in this study for all patients who complete at least 52 weeks of treatment with prophylactic emicizumab and still deriving clinical benefit for 3 years after last Arm D patient completes 1 year of treatment. *Extension phase may end earlier, before 3 years after the last Arm D patient completes 1 year treatment, should a post-trial continued access solution be available earlier.*

The approximate length of the entire study from screening of the first patient to the end of the study (including Arm D and study Extension Phase) will be approximately 88 months.

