4.5.7 Patient-Reported Outcomes

To capture bleed and hemophilia medication use data, as well as HRQoL and health status data during study treatment, patients/caregivers will complete the Bleed/Medication questionnaires on an electronic, handheld device that will be provided to them during their Week 1 visit at the site. This device will remain with the patients/caregiver for the duration of the study to enter bleed and medication data on a weekly basis at minimum *before the study extension phase. After the start of the extension phase, bleed and medication data will not be collected.* Patients and/or caregivers will complete HRQoL, proxy HRQoL-SF, and aspects of caregiver burden questionnaires at designated timepoints during clinic visits on a separate electronic, handheld device (tablet) that will remain at sites. The electronic, handheld device and instructions for completing the questionnaires will be provided by the investigator staff. The questionnaires should be completed by the patient or their caregivers at the site at the start of the visit and prior to all other study assessments.

After bleed, medication, HRQoL, proxy HRQoL, and aspects of caregiver burden entries have been saved, the data will be transmitted automatically from the respective devices to a centralized vendor database. Bleed and medication use data entered since the

patient's previous clinic visit will be reviewed at subsequent clinic visits, as per the schedule of assessments, for completeness and accuracy. Investigators will review the bleed and bleed medication data as per the schedule of assessments (see [Appendix 1](#)) and have the ability to correct or complete entries once verified with the patient/caregiver using a Data Change Request Form process or via a Web-based portal, once implemented.

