**Figure 1 Study Schema for Study YO39309**

BR = bleed rate; mo = month.

The primary efficacy analysis, defined as comparing the number of bleeds over time for patients randomized to receive prophylactic emicizumab versus no prophylaxis will be conducted after reaching the clinical cutoff, which occurs at the earliest timepoint when all randomized patients (Arms A, B, and C) have either completed 24 weeks in the study or discontinued from the study.

To obtain additional safety and efficacy data on emicizumab, patients who are randomized to the no prophylaxis arm (control arm, Arm Ccontrol) will have the opportunity to switch after 24 weeks to receive emicizumab prophylaxis at the Arm B dosing regimen (emicizumab prophylaxis at 3 mg/kg QW subcutaneously for 4 weeks, followed by 6 mg/kg Q4W). For clarity, Arm C patients during the no prophylaxis period are designated Ccontrol; whereas, after switch to emicizumab they are designated Arm Cemi. After completing at least 24 weeks of treatment with prophylactic emicizumab, patients who receive emicizumab prophylaxis (Arms A, B, or Arm Cemi after treatment switch) and derive clinical benefit will be allowed to continue emicizumab until marketing authorization as part of this study or a separate extension study, as long as they continue to derive clinical benefit and emicizumab is still in clinical development.

Those who are well controlled after 24 weeks on emicizumab (< 2 spontaneous and clinically significant bleeds) will continue treatment on their assigned emicizumab regimen; whereas, those who experience suboptimal control ( $\geq 2$  spontaneous and

clinically significant bleeds) will have the option to escalate to 3 mg/kg QW after approval from the Medical Monitor.

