## **2.2           COLLECTION OF PATIENT-REPORTED DATA**

### **2.2.1       Collection of Bleed and Medication Data**

Bleed and medication data are collected through an electronic bleed and medication questionnaire (BMQ), which was developed by the Sponsor given that no standard questionnaire for collection of these data exists.

The BMQ was developed as a patient-reported measure of bleeding episodes (including start date and time, reason, type, location, and symptoms of bleeds) and hemophilia-related medication use (i.e. start date and time, reason, type, and dose of injection).

To capture bleed data, emicizumab use, and other hemophilia medication use during study treatment, patients will complete the BMQ on a handheld device that will be provided to them during the Week 1 visit at the study site. This device will remain with the patient for the duration of the study to enter bleed and medication data as soon as bleeding event occurs. In the event of no bleed or medication use, the patient should complete the questionnaire at least weekly at a minimum. In case a patient did not experience any bleeds or administer any treatments for a week, the patient is asked to log into the device and fill in the questionnaire to confirm this. These weekly entries, in addition to the bleeds and medication entries, can also be used to assess compliance. Of note, the patient is able to enter bleeds and medications for the past 8 days, including the day the entries are made. This retrospective data entry window was considered acceptable in terms of recall bias and was added in order to optimize the completeness of data collection.

Patients who withdraw from emicizumab treatment will continue to record bleeds and hemophilia medication administration until they complete the safety follow-up visit.

The patient is able to edit and delete bleeds and medications for 24 hours after they are entered. Furthermore, the investigator and patient are instructed to review the data together at every clinic visit. If the patient has been unable to enter data for any reason, the investigator is able to do so using a data clarification request (DCR; not subject to the previous 8-day data entry window). Note, the symptoms of joint and muscle bleeds are not collected in this case because the patient may not be able to reliably remember them. In addition, the investigator is able to request a change be made to the vendor's database by submitting a DCR.

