#### **2.3.1.1 Efficacy Period**

The start of the efficacy period for each individual patient is defined as the first day when there is data in the BMQ. For patients starting the study on emicizumab (Arms A and B) this is expected to coincide with the Week 1 visit, and the day of their first emicizumab dose. For patients who do not start the study on emicizumab (Arm C), the start of the efficacy period should coincide with the Week 1 visit.

Of note, the first day when there is data in the BMQ, includes the first day for which data is reported via the handheld device, a DCR, or the day of device activation.

A second efficacy period is defined for patients in Arm C who switch to emicizumab starting on the day of their first emicizumab dose.

For patients randomized or enrolled on emicizumab, the end of the efficacy period is defined as the date of the clinical cutoff or the date of withdrawal from the initial study period (i.e., treatment phase according to eCRF), whichever is earlier. For patients randomized to no prophylaxis (Arm C), the end of the first efficacy period is defined as the day before the first emicizumab dose or the date of withdrawal from the initial study period (i.e., treatment phase according to eCRF) or the date of the clinical cutoff if neither of the aforementioned events has taken place. For patients whose dose is up-titrated, the efficacy period on the initial dose (the initial period for patients randomized to Arms A and B; the second efficacy period, starting at first emicizumab

dose for patients randomized to Arm C) ends 1 day prior to the first day on the up-titrated dose.

For patients who withdraw from the study before reaching the Week 1 visit, the duration of the efficacy period is set to 1 day, and it starts and ends on the same day of randomization/enrollment.

For patients whose dose is up-titrated, the bleeds on the up-titrated dose are analyzed separately. The efficacy period on a given up-titrated dose (second efficacy period for patients randomized to Arms A and B; third efficacy period for patient randomized to Arm C) starts with the first day on this dose and ends on the day of the clinical cutoff or the date of withdrawal.

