Withdrawal of consent

Lost to follow-up

– **Length of Study**

The approximate length of the entire study from screening of the first patient to the end of the study will be approximately 22 months.

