### **Schedule of assessments and schedule of samples**

The schedule of assessments and schedule of pharmacokinetic, immunogenicity, and biomarker samples are available in the Protocol version 3 (appendices 1 and 2, respectively).

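### The SAP's emicizumab efficacy periods have no stop when bleed recording ends at the extension phase, so an end-of-study cutoff would bias descriptive bleed rates low

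*SAP*

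**What the plan says.** **The SAP's period rules (2.3.1.1).**
- Arms A and B, assigned dose: "end of the efficacy period is defined as the date of the clinical cutoff or the date of withdrawal from the initial study period", whichever comes first. The SAP glosses that period as the treatment phase recorded in the eCRF.
- After up-titration, the new period "starts with the first day on this dose and ends on the day of the clinical cutoff or the date of withdrawal". The treatment-phase gloss is absent here.
- For Arm C after the switch, a start is given, but the only end given is the day before up-titration.

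**What the period is used for.** SAP 4.5.1 uses its length both as the ABR denominator and as the offset in the negative binomial model.

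**Cutoffs.** SAP Section 2 defines one clinical cutoff, for the primary analysis: "which occurs at the earliest timepoint when all randomized patients (Arms A, B, and C) have either completed 24 weeks in the study", with early leavers counted as done. SAP 2.5 adds a final analysis at the protocol-defined end of study and gives no cutoff date for it.

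**The protocol version behind the SAP.** SAP Appendix 1 notes that the assessment schedules "are available in the Protocol version 3" and that the study length "from screening of the first patient to the end of the study will be approximately 22 months". Continuing patients were to move to a separate extension study. SAP 2.2.1 accordingly has the bleed device "remain with the patient for the duration of the study to enter bleed and medication data".

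**The current protocol.** Section 3.2.2 gives a length ("including Arm D and study Extension Phase) will be approximately 88 months"). Patients with at least 52 weeks on drug and continuing benefit enter an extension inside this study. Section 4.5.7 states: "After the start of the extension phase, bleed and medication data will not be collected". Section 4.5.8.2 repeats this.

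**The concern.** Under Version 3, ending the period at cutoff or withdrawal was safe, because bleeds were recorded for as long as a patient was in the study. Under the current protocol, recording stops at extension entry while time in the study continues. Nothing in SAP 2.3.1.1 ends the efficacy period at that point.

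With an end-of-study cutoff, extension time would enter the denominator with no bleeds able to enter the numerator. The offset cannot correct this, because it is the same period length. The error can run only one way, towards lower bleed rates on emicizumab.

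The outputs at risk are descriptive: the efficacy summaries for all emicizumab patients (SAP 4.1) and the separate analysis of the up-titrated dose.

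**Working it through.** **Plan's own figure.** The documents give no figure for this point. The stated power (above 90%) belongs to the primary analysis. With variance = 10 × mean on the annual scale, the dispersions are 2.25 and 0.5. Then SE² = (1/(4 × 0.5) + 2.25)/28 + (1/(18 × 0.5) + 0.5)/14 = 0.142, so SE = 0.377, and power = Φ(ln(18/4)/0.377 − 1.96) = 97.9%. Other readings of the variance assumption give lower values (84.2% if it applies to the 24-week count). Nothing below depends on this figure.

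**Do other rules catch the gap?**
- SAP 4.9 treats the bleed data as complete, so it makes no adjustment.
- The first-24-weeks truncation in SAP 4.5.4 applies to the randomized comparisons only.
- Protocol Appendix 1-B keeps the handheld device in use for emicizumab dosing in the extension, so device activity would not mark the end of bleed recording.

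**Formula, if the cutoff is the end of study.** Reported rate = true rate × recorded time / counted time.

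**Inputs.**
- Study end: month 88 (protocol 3.2.2).
- Earliest extension entry: 52 weeks on drug, taken as 12 months (protocol 3.1).
- Late entry: month 88 − 36 = 52, when the 3-year clock starts.
- Assumed: first emicizumab dose in months 1 to 11, and staying in the study on drug to the end.

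**Assigned dose.** Counted time is 88 − 1 = 87 months to 88 − 11 = 77 months.

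| Extension entry | First dose month 1 | First dose month 11 |
|---|---|---|
| Week 52 | 12/87 = 0.14 | 12/77 = 0.16 |
| Month 52 | 51/87 = 0.59 | 41/77 = 0.53 |

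Applied to the planning ABR of 4 (SAP 2.4), the reported rate would be 4 × 12/87 = 0.55 to 4 × 51/87 = 2.34.

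**If the extension ends after one year (month 64).** Entry at Week 52 gives 12/63 = 0.19 to 12/53 = 0.23. Entry at month 52 gives 41/53 = 0.77 to 51/63 = 0.81.

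**Up-titrated dose, assuming up-titration at Week 24 (24/52 × 12 = 5.5 months) and the period run to month 88.** Counted time is 87 − 5.5 = 81.5 to 77 − 5.5 = 71.5 months. Entry at Week 52 leaves 12 − 5.5 = 6.5 recorded months: 6.5/81.5 = 0.08 to 6.5/71.5 = 0.09. Entry at month 52 gives 35.5/71.5 = 0.50 to 45.5/81.5 = 0.56.

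**Does the offset help?** A negative binomial fit with offset to 20,000 simulated patients per case, true ABR 2.4, first doses in months 1 to 11 and entry at month 52, returned 1.32 to 1.35 on counted time (ratio about 0.56). On recorded time the fits returned 2.35 to 2.42.

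**After the fix.** Counted time equals recorded time, and the factor is 1.00.

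**If the primary cutoff is kept instead.** The factor is also 1.00, but bleeds recorded between that cutoff and extension entry are omitted.

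**The case against.** The strongest case against is that the harm needs a cutoff the SAP never sets. The only defined cutoff is the primary one, and with it there is no dilution. Protocol 3.3.4 makes end-of-study efficacy analyses optional, the extension is described as serving continued treatment and safety data, and SAP 2.5 does not name bleed endpoints. This stands, and it makes the bias conditional. It does not remove the gap: SAP 2.5 plans a final analysis without excluding bleed endpoints, SAP 4.1 anticipates longer follow-up, and keeping the primary cutoff has its own cost in unused data.

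Second, the assigned-dose period is tied to the treatment phase in the eCRF, and the extension has its own Day 1, consent and schedule. Extension entry could therefore be treated as leaving that phase. That is arguable, but the SAP speaks of withdrawal and does not mention the extension. The up-titrated rule lacks even this link, so the gap is clearest there. Against that, the SAP expects few up-titrations, and Appendix 1-B lists only assigned-arm doses in the extension, so continued dosing at 3 mg/kg QW there is not described.

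Third, SAP 4.3 reviews observation time and device compliance, which may expose unrecorded time. It gives no rule for removing that time from the denominator.

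**Conclusion.** The point holds as a conditional one. SAP 2.3.1.1 was not brought into line with the end of bleed collection in the current protocol. With an end-of-study cutoff, descriptive emicizumab bleed rates would be biased low. With the primary cutoff they would be undiluted but would leave out recorded bleeds. The SAP does not say which applies. It should be fixed, but it is not a threat to the trial's main conclusion.

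The sizes are illustrative. They rest on assumed first-dose months, extension entry dates and retention on drug, none of which the documents give. Entry at Week 52 and at month 52 are the two extremes used.

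Three stronger readings are not supported:
- **That the primary result is inflated.** Its cutoff is the 24-week timepoint and the Arm C control period ends at the switch, so neither it nor the testing hierarchy is touched.
- **That each patient has a personal 3-year extension, giving 52 of 208 weeks (25%).** The extension ends at one calendar point, 3 years after the last Arm D patient completes 1 year. That ratio fits the last Arm D patient, whom this SAP does not cover.
- **That diluted values can be judged against the interval around the ABR of 2.4 in protocol 1.2.2.2.** That is a group interval from another study, and the factors here are for individual patients.

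**What to change.** 1. SAP 2.3.1.1: end every emicizumab efficacy period (assigned dose, Arm C after the switch, up-titrated dose) at the earliest of the clinical cutoff for that analysis, withdrawal, the day before up-titration where applicable, and the day before Extension Phase Day 1.
2. SAP 2.5: state the clinical cutoff for the final analysis.
3. SAP 2.2.1: say that bleed and medication entry runs until the extension phase starts, as in protocol 4.5.7.

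The cost is a few sentences in the SAP. It needs no protocol change and no new data, and it does not affect the primary analysis.

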### **2.3.1.2      Treated Bleed**

A bleed is considered to be a “treated bleed” if it is directly followed (i.e., there is not an intervening bleed) by a hemophilia medication reported to be a “treatment for bleed,” irrespective of the time between the treatment and the preceding bleed. A bleed and the first treatment thereafter are considered to be pairs (i.e., one treatment belongs to one bleed only), with the following exception: if multiple bleeds occur on the same calendar day, the subsequent treatment is considered to apply for each of these multiple bleeds (which are, however, counted as separate bleeds).

Bleeds due to surgery/procedure are not included in the primary analysis. Only treatments that were recorded as “treatment for bleed” are included in the determination of a treated bleed.

### **72-Hour Rule**

Two bleeds of the same type (e.g., “joint,” “muscle,” or “other”) and at the same anatomical location are considered to be one bleed if the second occurs within 72 hours from the last treatment for the first bleed. The last treatment is defined as the last treatment before a new bleed occurs, either in the same or in a different location. This is in-line with the above definition that bleeds and treatments are considered to be pairs.

### **2.3.2      Secondary Efficacy Endpoints**

The same definition of the efficacy period applies to all bleed-related secondary efficacy endpoints.

#### **2.3.2.1      All Bleeds**

“All bleeds” comprises both treated and non-treated bleeds. In this definition, all bleeds are included, irrespective of treatment with coagulation factors, with the following exception: bleeds due to surgery/procedure are excluded as for the primary analysis.

The endpoint of all bleeds fulfills the adapted ISTH criteria, as described in the protocol for the primary endpoint and the 72-hour rule, in particular. For treated bleeds, it is

implemented exactly as defined for the primary endpoint. For non-treated bleeds (not followed by any treatments with coagulation factors before the recording of a subsequent bleed), it is implemented by calculating a treatment-free period of 72 hours from the bleed itself.

### **2.3.2.2 Treated Spontaneous Bleeds**

In the analysis of spontaneous bleeds, only treated bleeds that fulfill the 72-hour rule are included.

Bleeds are classified as “spontaneous” if there is no other known contributing factor such as trauma or procedure/surgery.

### **2.3.2.3 Treated Joint Bleeds**

In the analysis of joint bleeds, only treated bleeds that fulfill the 72-hour rule are included. Bleeds due to procedure/surgery are again excluded.

Joint bleeds are defined as bleeds where the bleed type is “joint” as reported in the BMQ and is reported to have an unusual sensation (“aura”) in the joint in combination with at least one of the following symptoms: increasing swelling or warmth of the skin over the joint; and/or increasing pain, progressive loss of range of motion or difficulty in using the limb compared with baseline.

### **2.3.2.4 Treated Target Joint Bleeds**

Target joints are joints into which repeated bleeds occur (i.e.,  $\geq 3$  bleeds into the same joint over the last 24 weeks prior to study entry). The target joints prior to study entry are identified through the eCRF. The bleeds in target joints during the efficacy period are defined by first selecting the bleeds that fulfill the definition of a treated joint bleed and then counting how many of these occurred in a target joint as defined prior to study entry. The locations to be taken into account are shoulder, elbow, wrist, hip, knee, ankle. Left and right sides of the same joint type are considered to be separate joints.

### **2.3.2.5 Haem-A-QoL at 24 Weeks**

The Haem-A-QoL and the Haemo-QoL-SF will be used to measure HRQoL in adults and adolescents, respectively. Therefore, all calculations and analyses will be conducted separately for these two measures. Total score and physical health subscale score for the Haem-A-QoL will be evaluated at 24 weeks in the study and formally analyzed as described in the efficacy analysis section. However, only the physical health subscale will be part of the hierarchical testing procedure highlighted in this analysis section. Other subscale scores will be analyzed in a descriptive way.

The number of adolescent patients of the study will likely to be too small to provide meaningful statistical analyses of the Haemo-QoL-SF and therefore the analysis of this endpoint may only be descriptive.

### **2.3.2.6      EQ-5D-5L at 24 Weeks**

The European Quality of Life-5 Dimensions-5 Levels (EQ-5D-5L) index utility score using the U.K. value set and visual analogue scale (VAS) will be evaluated at 24 weeks in the study. These two endpoints will be analyzed as described in the efficacy analysis section but will not be part of the hierarchical testing procedure.

### **2.3.3      Exploratory Efficacy Endpoints**

The exploratory efficacy endpoints are as follows:

- Number of days away from school/work
- Number of days hospitalized

### **2.3.4      Pharmacokinetic Endpoints**

For patients treated on weekly dosing schedule, the pharmacokinetic (PK) endpoint for this study is the exposure (trough plasma concentration) to emicizumab at the following timepoints:

- Every week during weeks 1–4 on emicizumab
- Every 2 weeks during weeks 5–8 on emicizumab
- Every 4 weeks during weeks 9–24 on emicizumab
- Every 8 weeks during weeks 25–48 on emicizumab
- Every 12 weeks thereafter while on emicizumab until the end of the study

For patients treated on every 4 weeks dosing schedule, the PK endpoint for this study is the exposure (trough plasma concentration) to emicizumab at the following timepoints:

- Every week during week 1–4 on emicizumab
- Every 4 weeks during weeks 5–24 on emicizumab
- Every 12 weeks thereafter while on emicizumab until the end of the study

